#### b) Hand-held Dynamometer (HHD)

Neck flexion will be assessed using a HHD, another valid and reliable QMT tool for objectively quantifying muscle strength. (26, 27) HHD is a portable device which measures the MVIC of specific muscle actions. HHD has been selected for measuring the MVIC of neck flexion because it is easier to assess this muscle movement through a hand-held device rather than straps as in QMA.

Template No.: RWI\_TP\_EPI0011 Revision 2 Reference: RWI\_WI\_EPI0005

ARMGO Pharma, Inc. RYR1-RM Study Version 4.0 dated 10-SEP -2024 Protocol/Study No.: CL-EPI-001

Page 28 of 64

The procedure involves the participant pushing maximally against the device using a specific muscle movement for three to five seconds, while the tester applies a force to just overcome the strength of the participant, and the maximum force exerted by the muscle is recorded. (28) Each muscle action is assessed in a gravity-neutralized position. The specific testing position for testing neck flexion using HHD is described in Table 4.

Table 4. Position for the HHD measurement of neck flexion

Muscle movement	Position of participant	Dynamometer position	
Neck flexion	Sitting upright; head up at 90° from	Centre of forehead, just above eyebrows	
	horizontal		

HHD, Hand-held dynamometry. Source: van der Ploeg et al. (27)

HHD will be conducted at Screening, Visit 1, Visit 2, and End of Study Visit. Three measurements of neck flexion will be performed at each visit, and both the individual and average scores of the three measurements will be described. The raw scores are expressed in Newtons (and can be converted into Pounds or Kilograms) and will be compared against normative values derived from healthy individuals. (27)

## c) Manual Muscle Testing (MMT)

Neck flexion will also be measured using MMT, another validated and reliable tool that is designed to manually assess muscle strength and function. (10, 29) This method involves testing the strength of specific muscle movements based on their performance in relation to the forces of gravity or manual resistance through the available range of motion. The strength applied by the participant is then graded using a validated MMT scale (e.g., 5-point MRC or 10-point Kendall scale). In this study, the MMT assessment of neck flexion will be scored using the 5-point MRC scale for muscle strength (Table 5). (30)

Table 5. MRC scale for the MMT assessment of neck flexion

Muscle function	Grade	Strength level
No muscle activation	0	Zero
Movement in horizontal plane		
Trace muscle activation, such as a twitch, without achieving full range of motion	1	Trace

Template No.: RWI\_TP\_EPI0011 Revision 2 Reference: RWI\_WI\_EPI0005

ARMGO Pharma, Inc. RYR1-RM Study Version 4.0 dated 10-SEP -2024 Protocol/Study No.: CL-EPI-001

Page 29 of 64

Muscle activation with gravity eliminated, achieving full range of motion	2	Poor
Movement against gravity		
Muscle activation against gravity, full range of motion	3	Fair
Muscle activation against some resistance, full range of motion	4	Good
Muscle activation against examiner's full resistance, full range of motion	5	Normal

MMT, Manual Muscle Testing; MRC, Medical Research Council.

A description of the participant's and tester's position and procedure for assessing neck flexion using MMT is provided in Table 6. Of note, the test involves both an anti-gravity position and a gravity-eliminated position. The anti-gravity position should be tested first for all participants, while the gravity-eliminated position should only be tested in weaker participants who cannot move against gravity. (31) Further information about the test procedure can be found in the MMT manual. (32)

Template No.: RWI\_TP\_EPI0011 Revision 2 Reference: RWI\_WI\_EPI0005

ARMGO Pharma, Inc. RYR1-RM Study Version 4.0 dated 10-SEP -2024 Protocol/Study No.: CL-EPI-001

Page 30 of 64

Table 6. Position and procedure of the MMT assessment of neck flexion

Position in relation to gravity	Position of participant	Position of tester	Procedure
Anti-gravity	Supine, with arms by the side and head supported on a table	Standing next to the participant's head, with the testing hand placed on the participant's forehead	The participant lifts their head off the table by flexing the neck and tucking the chin. The tester applies resistance at the forehead in the direction of capital and cervical extension and may position a hand underneath the subject's head for protection or offer additional stabilization across the abdomen (if needed)
Gravity-eliminated (for weaker participants only)	Side lying, with head supported on the table and arms by the side	Supporting the participant's head to prevent cervical side bending, and providing stabilization at the anterior shoulder as needed	Participant is instructed to flex their head and neck towards their chest

MMT, Manual Muscle Testing. Source: MMT manual (32).

The MMT assessment of neck flexion will be conducted at Screening, Visit 1, Visit 2, and End of Study Visit. Three measurements of neck flexion will be performed at each visit, and both the individual and average scores of the three measurements will be described.

Although both MMT and HHD are designed to measure the same underlying concept, the literature only suggests moderate correlations between their measurements of neck flexion. (10) Such discrepancy may be explained by the fact that MMT has decreased sensitivity and specificity in detecting mild weakness compared to HHD. Furthermore, the grading system of MMT is subjective and may vary according to the strength of the examiner. (33, 34)

#### d) 10 Meter Walk Test (10-MWT)

This test will be used to assess walking speed in meters/second (m/s). A clear pathway of at least 10 meters (32.8 ft) in length in a designated area over solid flooring and a stopwatch will be required. A mark at 2m and 8m (identifying the central 6m which will be timed) will be

Template No.: RWI\_TP\_EPI0011 Revision 2 Reference: RWI\_WI\_EPI0005

ARMGO Pharma, Inc. RYR1-RM Study Version 4.0 dated 10-SEP -2024 Protocol/Study No.: CL-EPI-001 Page 31 of 64

marked. The total time taken to ambulate 6m will be recorded to the nearest hundredth of a second. 6m is then divided by the total time (in seconds) taken to ambulate and will be recorded in m/s. Two trials of the test should be conducted at the participant's comfortable walking speed, followed by two additional trials at their fast walking speed. (35)

In order to score the test, the time is measured for the middle 6m to allow for participant acceleration and deceleration. The tester should start recording the time when any part of the leading foot crosses the plane of the 2m mark, and the time is then stopped when any part of the leading foot crosses the plane of the 8m mark. (35)

The time to walk the middle 6m, the level of assistance, and type of assistive device and/or bracing used will be documented. If a participant requires total assistance or is unable to ambulate at all, a score of 0 m/s should be documented. The level of physical assistance is scored using an ordinal 7-point scale, as follows:

- 1 = total assistance (participant performs 0-24% of test);
- 2 = maximum assistance (participant performs 25-49% of test);
- 3 = moderate assistance (participant performs 50-74% of test);
- 4 = minimum assistance (participant performs 75-99% of test);
- 5 = supervision (participant requires stand-by or set-up assistance; no physical contact is provided);
- 6 = modified independent (participant requires use of assistive devices or bracing, needs extra time, mild safety issues); or
- 7 = independent.

The 10-MWT will be conducted at Screening, Visit 1, Visit 2, and End of Study Visit. The individual and average raw scores of each trial (expressed as m/s), as well as their deviation from normative values in healthy individuals (36), will be described.

#### e) 1-Minute Sit-to-Stand Test

The 1-Minute Sit-to-Stand Test will be used as an additional validated measure of the participants' muscular weakness. (12, 13) This test requires an armless chair, and the participant is instructed to perform as many sit-to-stand actions as possible in 1 minute without using the upper limbs.

The 1-Minute Sit-to-Stand Test will be administered at Screening, Visit 1, Visit 2, and End of Study Visit. Participants will undertake three trials at each visit. The number of sit to stands completed in one minute will be described for each trial (both individual and average scores per visit), along with their deviation from normative values. (12)

Template No.: RWI\_TP\_EPI0011 Revision 2 Reference: RWI\_WI\_EPI0005

ARMGO Pharma, Inc. RYR1-RM Study Version 4.0 dated 10-SEP -2024 Protocol/Study No.: CL-EPI-001 Page 32 of 64

#### f) 4 Stair Climb Test (4SCT)

Lastly, the 4SCT will be used to assess leg muscle power. The test equipment consists of a stopwatch and a flight of 4 stairs with rail. The participant will stand at the base of the stairs and will be required to ascend the stairs as fast as possible. Timing will start after the tester instructs the participant to start climbing and will stop when both participant's feet reach the top step. (15, 37)

This test will be administrated at Screening, Visit 1, Visit 2, and End of Study Visit, including three trails per visit. Stair climb power will be calculated using the following formula: power =  $[(body weight in kg) \times (9.8 \text{ m/s}^2) \times (stair height in meter)]/(time in seconds). (15, 37)$  The raw scores of the 4SCT will be expressed as Watts and will also be described as deviations from normative values. (38)

## 4.4.1.2 Secondary Endpoint Measures

The secondary endpoint measures evaluated in this study include a) the PROMIS Fatigue, PROMIS-PF, and IPAQ questionnaires, b) demographics and clinical characteristics of participants, and c) symptom diary.

#### a) PROMIS Fatigue, PROMIS-PF, and IPAQ questionnaires

PROMIS Fatigue (PROMIS-F): The PROMIS-F tool is a National Institutes of Health (NIH) developed Patient Reported Outcomes Measurement Information System (PROMIS) used to measure fatigue across a wide range of chronic health conditions. It has been used extensively and clinically validated across diverse chronic disorders. (39, 40). It can be administered as a Computerised Adaptive Test (CAT) or in various fixed length short forms. The PROMIS Short Form v1.0 Fatigue 7a (PROMIS F-SF 7a) is a reliable and valid 7-item questionnaire which has been evaluated across various populations, and it will be used to assess fatigue in this study (see Appendix 11.2). (41, 42) Using this measure, the participant is expected to respond to questions on symptoms over a period of 7 days prior to administration of the form. Each question has five response options ranging in value from one to five. Scores are represented as 'Never'-1, 'Rarely'-2, 'Sometimes'-3, 'Often'-4, and 'Always'-5. A total raw score for the short form with all questions answered is a sum of the values of the response to each question. The lowest possible raw score is 7; the highest possible raw score is 35. Using a score conversion table provided in the user manual, raw scores are translated into a T-score for each participant. The T-score rescales the raw score into a standardized score with a mean of 50 and a standard deviation (SD) of 10. (42) Higher PROMIS T-scores indicate higher fatigue. A PROMIS T-

Template No.: RWI\_TP\_EPI0011 Revision 2 Reference: RWI\_WI\_EPI0005

ARMGO Pharma, Inc. RYR1-RM Study Version 4.0 dated 10-SEP -2024 Protocol/Study No.: CL-EPI-001 Page 33 of 64

score higher than 50 represents more fatigue than the general population. Conversely, a T-score lower than 50 indicates less fatigue than the average. All questions must be answered in order to produce a valid score using the scoring tables provided in the measure specific scoring guide. For any unanswered questions, the Health Measures Scoring Service can be used to generate a final total score for participants with missing responses. The Health Measures Scoring Service is a web-based application that scores an Excel file of raw participant responses and returns by email a file with calculated T-scores for all measures including fields with missing responses. It is free to use but requires registration on the site in order to download an Excel file to input responses from the specific PROMIS measure and upload onto the service for the T-scores to be calculated. (42) The approach for dealing with the possible presence of item-level missing values in the data collected through the questionnaires will be further outlined in the SAP.

PROMIS Physical Function (PROMIS-PF): The PROMIS-PF is used to measure physical functioning and is efficient and sensitive to changes across a broad range of functioning in chronic disease conditions. The PROMIS-PF can be administered as a CAT, or as a stand-alone Short Form. In this study, the 10-item PROMIS Short Form v2.0 Physical function 10a (PROMIS PF-SF 10a) will be used (Appendix 11.3). (43) This short form has been validated in similar populations in previous studies. (40) It includes 10 questions, with five possible responses for each question. For the first set of five questions, response options are represented as 'Not at all' -5, 'Very little' - 4, 'Somewhat' -3, 'Quite a lot' 2, and 'Cannot do' -1. For the second set of five questions, the response options are, 'Without any difficulty' -5, 'With a little difficulty' - 4, 'With some difficulty' -3, 'With much difficulty' -2, and 'Unable to do' -1. The lowest possible score is 10 and the highest possible score is 50. (44) This scale can be scored either using the Health Measures Scoring Service, a data collection tool to automatically calculate participant scores, or using raw summed scores as detailed in the measure specific scoring guide. (44) The raw summed scores method will be used in this study. For this measure, as with the PROMIS F-SF, a total raw score for the short form with all the questions answered will be calculated for each participant and converted to a T-score using a score conversion table provided in the user manual. (44)

International Physical Activity Questionnaire (IPAQ): This questionnaire is a self-reported measure of physical activity and has been validated in a previous multi-country study. (45) The questionnaire is divided into domains with questions on vigorous physical activity, moderate physical activity, time spent walking, and time spent sitting over the previous 7-day time period. The IPAQ Short Form will be used in this study (IPAQ-SF; see Appendix 11.4). Two forms of output can be generated from scoring the IPAQ. Results can either be reported in categories (low, moderate or high activity levels) or as a continuous variable indicating Metabolic Equivalent (MET) minutes a week. Physical activity levels will be described as both continuous (in MET minutes per week) and as categories (low, moderate and high) in this study. MET

Template No.: RWI\_TP\_EPI0011 Revision 2 Reference: RWI\_WI\_EPI0005

ARMGO Pharma, Inc. RYR1-RM Study Version 4.0 dated 10-SEP -2024 Protocol/Study No.: CL-EPI-001

Page 34 of 64

minutes represent the amount of energy expended carrying out physical activity. One MET is what is expended when an individual is at rest, and two METS is twice what is expended at rest. To get a continuous variable score from the IPAQ (MET minutes a week), walking is considered to be 3.3 METS, moderate physical activity 4 METS, and vigorous physical activity 8 METS. (46) Scores are categorised into three categories (high, moderate and low). The specific criteria used for scoring the IPAQ are showed in Table 7. (46)

Table 7 Scoring for International Physical Activity Questionnaire (46)

Scoring Categories	Criteria
High	Vigorous intensity activity on at least 3 days achieving a minimum total physical activity of 1500 MET minutes a week.
	OR
	7 or more days of any combination of walking, moderate intensity or vigorous intensity activities achieving a minimum of at least 3000 METS minutes a week.
Moderate	3 or more days of vigorous intensity activity and/or walking of at least 20 minutes per day.
	OR
	5 or more days of moderate intensity activity and/or walking for a minimum duration of 30 minutes per day.
	OR
	5 or more days of any combination of walking, moderate intensity or vigorous intensity activities achieving a minimum total physical activity of at least 600 MET minutes a week.
Low	If criteria for high or moderate categories are not met.

To calculate MET minutes in a week, the MET value given number (walking = 3.3, moderate activity = 4, vigorous activity = 8) is multiplied by the minutes the activity was carried out for and by the number of days that that activity was undertaken. For example, if someone reports walking for 30 minutes 5 days a week, then the total MET minutes for that activity are  $3.3 \times 30 \times 5 = 495$  MET minutes a week). (46) MET minutes achieved in each category (low, moderate, and high activity) can be summed to get total MET minutes of physical activity per week.

Template No.: RWI\_TP\_EPI0011 Revision 2 Reference: RWI\_WI\_EPI0005

ARMGO Pharma, Inc. RYR1-RM Study Version 4.0 dated 10-SEP -2024 Protocol/Study No.: CL-EPI-001

Page 35 of 64

The PROMIS-F, PROMIS-PF, and IPAQ questionnaires will be completed by the participants at Screening and End of Study visits. Details on domains measured using the above mentioned questionnaires are given in

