## **Table 8 Questionnaires**

Measures	Dimensions	
PROMIS-Fatigue SF v1.0	Frequency of feeling tired	
7a	
 
Frequency of experiencing extreme exhaustion
 
	
	
 
Frequency of running out of energy
 
	
	
 
Frequency of fatigue limiting to work (include work at home)
 
	
	
 
Frequency of feeling too tired to think clearly
 
	
	
 
Frequency of feeling too tired to take a bath or shower
 
	
	
 
Frequency of having enough energy to exercise strenuously
 
	
PROMIS-PF-SF 10a Item	• Being able to dress oneself, including tying shoelaces and doing	
Short Form (Covers Self-	buttons	
care and Lower Extremity)	
 
Being able to shampoo hair
 
	
	
 
Being able to wash and dry body
 
	
	
 
Being able to get on and off the toilet
 
	
	
 
Being able to do chores such as vacuuming or yard work
 
	
	
 
Health limiting in bending, kneeling, or stooping
 
	
	
 
Health limiting in lifting or carrying groceries
 
	
	
 
Health limiting in climbing one flight of stairs
 
	
	
 
Health limiting in walking more than a mile
 
	
	
 
Health limiting in doing vigorous activities
 
	
Additional Item on	
 
Do you have difficulties turning in bed or moving in bed?
 
	
Physical Function		

Template No.: RWI\_TP\_EPI0011 Revision 2 Reference: RWI\_WI\_EPI0005

ARMGO Pharma, Inc. RYR1-RM Study Version 4.0 dated 10-SEP -2024 Protocol/Study No.: CL-EPI-001

Page 37 of 64

Measures	Dimensions
IPAQ 7 Item Short Form	Number of days doing vigorous physical activities like heavy lifting,
(covers past 7 days)	digging, aerobics, or fast bicycling
	Amount of time per day doing those vigorous physical activities
	Number of days doing moderate physical activities like carrying light
	loads, bicycling at a regular pace, or doubles tennis
	Amount of time per day doing those moderate physical activities
	
 
Number of days walking for at least 10 minutes at a time
 

	Amount of time per day spending walking
	Amount of time per day spending sitting

IPAQ, International Physical Activity Questionnaire, PROMIS, Patient-Reported Outcomes Measurement Information System; PROMIS, Patient-Reported Outcomes Measurement Information System; PROMIS-PF, Patient-Reported Outcomes Measurement Information System-Physical Function.

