# 6.2.2.2 Secondary Objective Analysis

The PROMIS Fatigue, PROMIS-PF, and IPAQ questionnaires will be scored according to their manual instructions (see Section 4.4.1.2). PRO endpoints assessed through the PROMIS Fatigue, PROMIS-PF, and IPAQ questionnaires and the symptom diary will be summarized using appropriate descriptive statistics, as outlined in Section 6.2.1.

Demographic and clinical characteristics of participants and data collected through the diary will be summarized with descriptive statistics, as outlined in Section 6.2.1. AE endpoints recorded throughout the study will also be summarized through descriptive analysis.

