# Fatigue - Short Form 7a

Please respond to each question by marking one box per row.

In the past 7 days...

		Never	Rarely	Sometimes	Often	Always
FATEXP20	How often did you feel tired?		2	3	4	5
FATEXP5	How often did you experience extreme exhaustion?	Ī		3	4	5
FATEXPIS	How often did you run out of energy?		2	3	4	5
FATIMPSS	How often did your fatigue limit you at work (include work at home)?			3	4	5
FATIMP50	How often were you too tired to think clearly?			3	4	5
FATIMF21	How often were you too tired to take a bath or shower?		2	3	4	5
FATIMF40	How often did you have enough energy to exercise strenuously?	5	□ +	3	2	1

Template No.: RWI\_TP\_EPI0011 Revision 2 Reference: RWI\_WI\_EPI0005

ARMGO Pharma, Inc. RYR1-RM Study Version 4.0 dated 10-SEP -2024 Protocol/Study No.: CL-EPI-001 Page 63 of 64

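### Section 4.4.1.2 gives one forward key for all PROMIS Fatigue 7a items, but the Appendix 11.2 form scores the energy item in reverse

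*Protocol*

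**What the plan says.** Section 4.4.1.2 a) of the protocol describes the scoring of the seven-item form in four steps.

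- Scope: "Each question has five response options ranging in value from one to five".
- Key: "Scores are represented as 'Never'-1, 'Rarely'-2, 'Sometimes'-3, 'Often'-4, and 'Always'-5".
- Total: "A total raw score for the short form with all questions answered is a sum of the values of the response to each question". The range follows: "The lowest possible raw score is 7; the highest possible raw score is 35".
- Direction, after conversion to a T-score: "Higher PROMIS T-scores indicate higher fatigue".

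No item is named as an exception.

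Appendix 11.2 reproduces the form. Its last item asks "How often did you have enough energy to exercise strenuously". That row carries 5 under *Never* and falls to 1 under *Always*. The legible values on the other six rows rise to 5 under *Always*. Table 8 lists the same item among the dimensions of the form, as "Frequency of having enough energy to exercise strenuously", so it is part of the scored total.

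On which source governs, the secondary-objective paragraph of the Synopsis sends scoring to the questionnaire manuals. Section 6.2.2.2 does the same but adds a pointer: "questionnaires will be scored according to their manual instructions (see Section 4.4.1.2". That is the section holding the unreversed key.

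**The concern.** Six of the items ask about tiredness or its effects, so a frequent answer means more fatigue. The seventh asks about having energy, so a frequent answer means less. A single forward key counts that item against the direction the protocol states for the score.

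PROMIS Fatigue is a named secondary endpoint. It is collected at Screening and at the End of Study Visit, and the Rationale cites improvement on it in Phase 1. The study is meant to tell the sponsor what level and variability to expect in Phase II. A miskeyed item would distort both, and would feed a wrong raw sum into the T-score conversion. On that item alone, a gain in energy between the two visits would add to the fatigue score rather than reduce it.

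**Working it through.** **Inputs.** The text key, the sum rule and the 7 to 35 range come from Section 4.4.1.2. The reversed values come from the FATIMF40 row in Appendix 11.2. In the extracted text, the second value of that row is garbled and some digits in other rows are missing. The legible 5, 3, 2, 1 fix the sequence, and the second value is taken as 4. None of that damage is counted as an error.

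**Notation.** Let *x* = 1, 2, 3, 4, 5 for *Never* to *Always* on the energy item, and let *T* be the sum of the other six items, which are scored forward under both keys.

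- Text key: raw score = *T* + *x*
- Form key: raw score = *T* + (6 - *x*)
- Text minus form = *x* - (6 - *x*) = 2*x* - 6

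**The protocol's own range.** Text key: minimum 7 × 1 = 7, maximum 7 × 5 = 35. Form key: minimum 6 × 1 + (6 - 5) = 7, maximum 6 × 5 + (6 - 1) = 35. The stated range is right under both keys, so an out-of-range check on the total cannot tell them apart.

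**Error per participant.**

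| Energy answer | Text | Form | Text - form |
|---|---|---|---|
| Never | 1 | 5 | -4 |
| Rarely | 2 | 4 | -2 |
| Sometimes | 3 | 3 | 0 |
| Often | 4 | 2 | +2 |
| Always | 5 | 1 | +4 |

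Four of the five possible answers give a different total. That is 80% of all possible response patterns, which is not a forecast of 80% of participants.

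**Anchor patterns.**

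- Most fatigued (six items *Always*, energy *Never*): text 6 × 5 + 1 = 31; form 6 × 5 + 5 = 35.
- Least fatigued (six items *Never*, energy *Always*): text 6 × 1 + 5 = 11; form 6 × 1 + 1 = 7.
- Distance between the two anchors: 31 - 11 = 20 by the text, 35 - 7 = 28 by the form.

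**Ordering.** Take two participants who answer *Sometimes* to the six tiredness items (*T* = 18). One never has energy for strenuous exercise: text 19, form 23. The other always does: text 23, form 19. The text key ranks the second as the more fatigued.

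**Group mean.** The shift is the mean of 2*x* - 6, or 2 × mean(*x*) - 6. It runs from -4 (all answer *Never*) to +4 (all answer *Always*) and is zero when mean(*x*) = 3. The bound is 4 of 28 raw points, 4/28 = 14% of the scale, in either direction.

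**Change between visits.** If the energy answer moves by Δ*x*, the text key adds Δ*x* and the form key subtracts it, so the change is off by 2Δ*x*. From *Never* to *Sometimes*, Δ*x* = 2: the form records -2, the text +2.

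**T-score.** The conversion table is not in the protocol, so the effect on the reported T-score cannot be calculated.

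**The case against.** The strongest defence is that the faulty line is only a summary and need never be used. Section 4.4.1.2 refers to Appendix 11.2 for the form. The form prints a value beside each answer, and anyone adding those printed values gets the right total. The Synopsis calls for manual scoring without any pointer back to the section text. Section 6.2.1 leaves derivation algorithms to the SAP, which is not at hand and may have the key right.

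Much of this stands. It means a wrong score is conditional: it arises only if the section text, rather than the form or the manual, drives programming or hand scoring. A reader might infer that the study's fatigue scores will be wrong, and the documents do not support that.

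It does not remove the inconsistency. This is not a detail left open for the SAP: the protocol states a specific key that its own form contradicts, and Section 6.2.2.2 directs the analyst to that key. For PROMIS Physical Function the same section spells out a separate key for each of the two item sets, so a reader has reason to take the Fatigue key as complete.

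Three other strong readings also fail:

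- *That mean fatigue would be understated because most participants never have energy for strenuous exercise.* The protocol gives no response distribution for this item. The error is symmetric and could go either way.
- *That the 7 to 35 range is wrong.* It is correct under both keys. The narrower 11 to 31 span applies only to the two consistent extreme patterns.
- *That improvement in fatigue would appear as worsening overall.* This holds for one item of seven. Whether the total moves the wrong way depends on the other six.

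**Conclusion.** The inconsistency is real. Section 4.4.1.2 applies one forward key to each question, Appendix 11.2 reverses the energy item, and only the appendix fits the stated direction of the score.

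The size given above assumes that the text key is the one applied: 0, 2 or 4 raw points per participant, and a mean shift of no more than 4 points either way, whose sign and amount depend on answers the documents do not give.

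Severity is moderate. The endpoint is secondary, summarised descriptively in up to 20 participants, and is neither an eligibility criterion nor part of the primary endpoint. If the marked answers are stored, every score can be re-derived. What lifts it above a matter of wording is that the error would leave totals inside the valid range and could go unnoticed.

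**What to change.** Add one sentence to Section 4.4.1.2: the item on energy for strenuous exercise (FATIMF40) is scored 5 for *Never* down to 1 for *Always*, as printed in Appendix 11.2, before the seven values are summed. Build the eCRF and the derivation to that rule, and store the answer marked as well as any numeric value.

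Test the program with two patterns: six items *Always* with energy *Never* must return 35, and six items *Never* with energy *Always* must return 7. A result of 31 or 11 shows that the unreversed key is in use.

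The cost is a sentence and two test cases. No change to the form, the visit schedule or the data collected from participants is needed.

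### The IPAQ Moderate category admits walkers at 198 MET-min/week, while every other way into it needs 480 to 600

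*Protocol*

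**What the plan says.** Protocol Section 4.4.1.2 a) scores the IPAQ Short Form in two ways, as MET-minutes per week and as a low, moderate or high category, and both are to be reported. The weights are given by activity type: "walking is considered to be 3.3 METS, moderate physical activity 4 METS, and vigorous physical activity 8 METS". Table 7 then sets the category rules. Moderate is reached by any one of three routes joined by OR:

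- Route 1: "3 or more days of vigorous intensity activity and/or walking of at least 20 minutes per day"
- Route 2: "5 or more days of moderate intensity activity and/or walking for a minimum duration of 30 minutes per day"
- Route 3: 5 or more days of any combination of activities, "achieving a minimum total physical activity of at least 600 MET minutes a week"

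Low is the residual class: "If criteria for high or moderate categories are not met".

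Below the table, a worked example multiplies weight, minutes and days for a walker. The paragraph then ends: "MET minutes achieved in each category (low, moderate, and high activity) can be summed to get total MET minutes of physical activity per week".

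IPAQ output is a named secondary endpoint (Section 3, Table 1). Section 6.2.2.2 says that the questionnaires are scored by their manuals and refers back to Section 4.4.1.2.

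**The concern.** Route 1 gives 20 minutes of walking the same credit as 20 minutes of vigorous activity, although the protocol weights vigorous activity about 2.4 times as heavily (8/3.3). Route 2 asks walkers for more days and longer walks than route 1 does. If route 1 is applied as printed, the stricter walking requirement has no effect on people who only walk.

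Low is whatever remains after High and Moderate, so a Moderate rule that is too wide can shift participants in one direction only, from Low to Moderate. The category table would then understate how many participants have low physical activity, in a cohort that must be able to walk 10 metres (Section 4.2.1).

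The sentence on the total is a separate and lesser matter. Low, moderate and high are classes of participant. The questionnaire has "questions on vigorous physical activity, moderate physical activity, time spent walking, and time spent sitting over the previous 7-day time period", and the MET weights belong to walking, moderate and vigorous activity.

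**Working it through.** **Inputs.** MET weights: walking 3.3, moderate 4, vigorous 8 (Section 4.4.1.2). Day, minute and MET thresholds: Table 7. The IPAQ Short Form records days per week and usual time per day for each activity (Table 8 and Appendix 11.4).

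**Formula.** MET-min/week = weight × minutes per day × days per week.

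**The protocol's own figure.** Its example runs "if someone reports walking for 30 minutes 5 days a week, then the total MET minutes for that activity are" 3.3 × 30 × 5 = 495. This reproduces exactly.

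**Minimum MET-min/week at each entry to Moderate.**

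| Route | Activity | Calculation | MET-min/week |
|---|---|---|---|
| 1 | Walking | 3.3 × 20 × 3 | 198 |
| 1 | Vigorous | 8 × 20 × 3 | 480 |
| 2 | Walking | 3.3 × 30 × 5 | 495 |
| 2 | Moderate | 4 × 30 × 5 | 600 |
| 3 | Any combination | stated | 600 |

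Walking under route 1 enters at 198/495 = 40% of the walking entry under route 2, and at 198/600 = 33% of the route 3 floor.

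**Participants who only walk.**

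- Route 2 needs at least 5 days and 30 minutes, so it always satisfies route 1 (3 days, 20 minutes).
- Route 3 needs at least 600/(3.3 × days) minutes per day: 36.4 on 5 days, 30.3 on 6 days and 26.0 on 7 days. All exceed 20, so it too always satisfies route 1.

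Enumerating walking-only weeks (1-7 days, 10-180 whole minutes per day) confirms this: no week meets route 2 or route 3 without meeting route 1.

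**Who is Moderate through route 1 alone.** These walking-only weeks would be Low under routes 2 and 3:

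| Days | Minutes per day | MET-min/week |
|---|---|---|
| 3-4 | 20 or more | from 198 (3 days) or 264 (4 days) |
| 5 | 20-29 | 330 to 478.5 |
| 6 | 20-29 | 396 to 574.2 |
| 7 | 20-25 | 462 to 577.5 |

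On 3-4 days the bar is the day count, not the volume: 4 days at 60 minutes is 3.3 × 60 × 4 = 792 MET-min/week and still fails routes 2 and 3.

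**Mixed weeks.** Take moderate activity for 30 minutes on 3 days and walking for 30 minutes on 2 other days.

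- Total: 4 × 30 × 3 + 3.3 × 30 × 2 = 360 + 198 = 558.
- Route 1 fails, with two walking days and no vigorous activity.
- Route 3 fails, because 558 is below 600.
- Route 2 is met, and only because walking counts there.

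So walking in route 2 is redundant for people who only walk, but not for everyone.

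**The total.** The formula and the 495 example work by activity type. Summing over walking, moderate and vigorous activity follows directly from them and leaves the example unchanged.

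**The case against.** Four points can be made in the plan's defence.

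1. *The routes are joined by OR, so nothing contradicts.* This stands. A reader might infer that Table 7 contradicts itself, but all three routes can be applied together. The defect is incoherence, plus redundancy for walking-only participants. Unequal floors alone prove little either: with walking removed from route 1 they would still be 480, 495 and 600. What stands out is one entry point far below all the others.

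2. *The mislabelled sum does no numerical harm.* This also stands. A reader might infer that it pushes categories upward. It does not: the weights, formula and example just before it are by activity type and correct, and they lead to only one workable sum.

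3. *The cited guideline may contain the clause, and scoring follows the manual anyway.* This stands in part. The protocol alone cannot show what the guideline says, so an unconditional deletion would go too far. But Table 7 is presented as the specific scoring criteria, and Section 6.2.2.2 sends the reader back to it, so the general reference to manuals does not clearly override it. Section 6.2.1 leaves derivation algorithms to the SAP; an SAP that follows Table 7 would carry the problem over.

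4. *The effect is small.* Largely right. The objective also has PROMIS Fatigue, PROMIS-PF and the continuous MET score, and no hypothesis is tested (Section 6.1).

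**Conclusion.** Wrong as written, with low impact. On the protocol's own weights, the walking alternative in route 1 lets participants into Moderate at 198 MET-min/week, against 480 to 600 elsewhere. It leaves routes 2 and 3 without effect for anyone whose only activity is walking. Any error runs one way, from Low to Moderate, and stays at that boundary. The High criteria and the continuous score do not use route 1.

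The number of participants affected cannot be computed, because the protocol gives no distribution of walking time; it could be zero. If all 20 planned participants are enrolled and evaluable, each one affected moves the Low and Moderate proportions by 1/20 = 5 percentage points. A reader might infer that the study will materially understate the reduction in activity, on the view that walking is these patients' main activity. The protocol does not say so, and that size of effect is not supported.

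**What to change.** Before the IPAQ derivation is programmed, check Table 7 against the scoring guideline it cites. Unless that guideline supports the clause, delete *and/or walking* from the first Moderate criterion, so that walking counts only under the second and third. If the guideline does support it, keep it and say so in the SAP.

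As a wording correction only, state that total MET-minutes per week are the sum over walking, moderate and vigorous activity.

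The cost is one phrase in the table, one sentence of text and a check of a source already cited. Data collection does not change, and the continuous score is the same before and after.
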